## C.8 Missing Data and Planned Sensitivity Analyses (Primary Objective)

Every effort will be undertaken to minimize missing data. However, some missingness is inevitable, and the study is designed with the expectation that there may be up to 6% missing primary data at 24 months. The reasons for missing data will be described in detail and evaluated for assessment of possible bias. The distribution of prognostic factors between patients with data and those without data will be examined to evaluate any potential sources of bias.

By design, the analysis of the primary objective (at both interim time points) will predict 24-month outcomes for any subjects without measured 24-month outcomes, based on transitions from interim states and the experience of those who went on from those states to provide complete 24-month data. This is true whether the missing 24-month outcomes are due to being accrued later in the trial (as happens for many subjects at the interim “win” analyses) or some other cause, such as loss to follow-up (which will likely apply at both the interim and final “win” analyses). Several additional analyses are planned to be conducted (at the conclusion of the trial) that will explore the sensitivity of the main conclusions to the predictions for subjects whose missing 24-month outcomes cannot be explained by simply being accrued late (ie., subjects who are known to be lost to follow-up or whose 24-month visit window has closed without a measured outcome). In these analyses and for such subjects, 24-month outcomes will be imputed according to the model described below.

As with the primary analysis, any such subject will be viewed as belonging to one of several interim states. These are the same states used in the primary analysis (eg., “E” or “P” or “N” at 6 months, etc.)

For each of these states, the probability of becoming a composite success at 24 months will be modeled via a logistic formulation. Based on the number of subjects who went on from that state to become 24-month “E” and “N” subjects, respectively, a logistic regression of the following form will be fit:

$$\text{logit}(p) = \beta_0$$

where the parameter  $\beta_0$  will be assigned a vague  $N(0,10^2)$  distribution. The posterior distribution for  $\beta_0$  will then be shifted by a biasing constant  $\gamma$  and will be back-transformed to the probability scale as:

$$p^* = \text{logit}^{-1}(\beta_0 + \gamma)$$

The 24-month outcome for any subject belonging to this state but lost thereafter will be imputed based on this distribution of  $p^*$ . The case  $\gamma = 0$  contains no bias and corresponds essentially to the primary analysis.

By varying  $\gamma$ , the impact of a biasing influence on the study results can be examined. The values  $\gamma = +\infty$  and  $\gamma = -\infty$  correspond to setting all such observations to be "E" or "N." The impact of various values of  $\gamma$  (including  $+\infty$  and  $-\infty$ ) will be examined and presented in a sensitivity analysis, representing both positive and negative biases for the two groups.

Further analyses will explore the sensitivity of efficacy to the imputation model. Specifically, one analysis will present posterior probabilities of non-inferiority/superiority without the use of prediction (ie., completers only). Another will present the results of a tipping point analysis.

## C.9 Description of Performed Analysis, per Population

### C.9.1 Analysis of screening population

For the screening population only descriptive statistical analysis will be performed, on variables that are captured in the EDC system.

### C.9.2 Analysis of ITT and mITT Populations

For the subjects in the randomized population the primary analysis of the primary endpoint and inferential statistics for the following secondary endpoints will be performed on the ITT and mITT populations:

- Major adverse cardiovascular and cerebrovascular events (MACCE)
- Individual MACCE components
- Major adverse events (MAE)
- Conduction disturbance requiring permanent pacemaker implantation
- NYHA
- Six-minute walk test
- Ratio of days alive out of hospital versus total days alive
- Quality of life
- Echocardiographic assessment of valve performance
- Aortic valve disease-related hospitalizations
- Cardiovascular deaths and valve-related deaths
- Strokes and TIAs
- Peri-procedural neurological injury
- Index procedure-related MAEs
- Length of index procedure hospital stay
- Device success
- Procedure success

### C.9.3 Analysis of implanted population

The endpoints listed in C.9.2 will also be performed on the implanted population. Additionally, the implanted population will be used for analyzing the primary endpoint, secondary endpoint of prosthetic valve dysfunction, and echocardiographic assessment of valve performance.

## C.10 Secondary Endpoints

The following secondary endpoints will be compared between TAVI and SAVR subject cohorts using the appropriate Bayesian version of analysis for comparing proportions and continuous variables as described below:

1. Incidence of Major Adverse Cardiovascular and Cerebrovascular Events (MACCE) at 30 days, 6 months, 12 months, 18 months, 24 months, and annually thereafter up to 5 years. MACCE is defined as a composite of:

- All-cause death
- Myocardial infarction (MI)
- All stroke, and
- Reintervention (defined as any cardiac surgery or percutaneous reintervention catheter procedure that repairs, otherwise alters or adjusts, or replaces a previously implanted valve)

MACCE-incidence estimates will be provided for the two treatment groups at 30 days, 6 months, 12 months, 18 months, 24 months, and annually thereafter up to 5 years. The statistical method will be the Bayesian version of a comparison of proportions (with predictions).

Additionally, incidence of MACCE will be compared at 30 days or hospital discharge, whichever is later. The statistical method will be the Bayesian version of a comparison of proportions

2. The occurrence of individual MACCE components at 30 days, 6 months, 12 months, 18 months, 24 months, and annually thereafter up to 5 years.

MACCE components will be summarized and their incidence estimates provided at 30 days, 6 months, 12 months, 18 months, 24 months, and annually thereafter up to 5 years. The statistical method will be the Bayesian version of a comparison of proportions (with predictions).

3. Major Adverse Events (MAE) and individual components of MAE at 30 days, 6 months, 12 months, 18 months, 24 months, and annually thereafter up to 5 years.

Major adverse event (MAE) includes:

- MACCE
- Acute kidney Injury
- Cardiac tamponade
- Prosthetic valve dysfunction – including moderate or severe aortic regurgitation
- Cardiogenic shock
- Prosthetic valve endocarditis
- Life-threatening, disabling or major bleeding
- Major vascular complication
- Cardiac perforation
- Valve malpositioning

MAE events and individual components of MAE will be summarized and the incidence of MAEs will be provided at 30 days, 6 months, 12 months, 18 months, 24 months, and annually thereafter up to 5 years. The statistical method will be the Bayesian version of a comparison of proportions (with predictions).

Additionally, incidence of major vascular complications and incidence of major or life-threatening bleeding events at 30 days or hospital discharge, whichever is longer, will also be compared using the Bayesian version of a comparison of proportions.

4. Incidence of Early safety at 30 days defined as a composite of:

- All-cause mortality
- All stroke (disabling and non-disabling)
- Life-threatening bleeding
- Acute kidney injury—Stage 2 or 3 (including renal replacement therapy)
- Coronary artery obstruction requiring intervention
- Major vascular complication
- Valve-related dysfunction requiring repeat procedure (BAV, TAVI, or SAVR)
- All-cause death

Early safety composite endpoint-incidence estimates will be provided for the two treatment groups at 30 days. The statistical method will be the Bayesian version of a comparison of proportions.

5. Incidence of Clinical Efficacy (after 30 days) at 6 months, 12 months, 18 months, 24 months and annually thereafter up to 5 years. Clinical efficacy defined as a composite of:
- All-cause mortality
  - All stroke (disabling and non-disabling)
  - Requiring hospitalizations for valve-related symptoms or worsening congestive heart failure
  - NYHA class III or IV
  - Valve-related dysfunction (mean aortic valve gradient  $\geq 20$  mmHg, EOA  $\leq 0.9$ - $1.1$  cm^2 and/or DVI  $< 0.35$  m/s, AND/OR moderate or severe prosthetic valve regurgitation\*)

Clinical efficacy estimates will be provided for the two treatment groups at 6 months, 12 months, 18 months, 24 months and annually thereafter up to 5 years. The statistical method will be the Bayesian version of a comparison of proportions (with predictions).

\*Refers to VARC-2 definitions

6. Incidence of Time-Related Safety at 30 days, 6 months, 12 months, 18 months, 24 months and annually thereafter up to 5 years. Time-Related Safety defined as a composite of:
- Structural valve deterioration:
    - Valve-related dysfunction (mean aortic valve gradient  $\geq 20$  mmHg, EOA  $\leq 0.9$ - $1.1$  cm^2 and/or DVI  $< 0.35$  m/s, AND/OR moderate or severe prosthetic valve regurgitation\*)
    - Requiring repeat procedure (TAVI or SAVR)
  - Prosthetic valve endocarditis
  - Prosthetic valve thrombosis
  - Thromboembolic events (e.g. stroke)
  - VARC bleeding, unless clearly unrelated to valve therapy (e.g. trauma)

Time related safety composite endpoint-incidence estimates will be provided for the two treatment groups at 30 days, 6 months, 12 months, 18 months, 24 months and annually thereafter up to 5 years. The statistical method will be the Bayesian version of a comparison of proportions (with predictions).

\*Refers to VARC-2 definitions

7. Conduction disturbance requiring permanent pacemaker implantation at 30 days, 6 months, 12 months, 18 months, 24 months, and annually thereafter up to 5 years.

The incidence of conduction disturbance requiring permanent pacemaker implantation will be provided at 30 days, 6 months, 12 months, 18 months, 24 months, and annually thereafter up to 5 years, separately for new onset and pre-existing conduction disturbance. The statistical method will be the Bayesian version of a comparison of proportions (with predictions).

8. Change in NYHA class from baseline at 30 days, 6 months, 12 months, 18 months, 24 months, and annually thereafter up to 5 years.

NYHA classifications will be summarized with frequencies and percentages at baseline, 30 days, 6 months, 12 months, 18 months, 24 months, and annually through five years. Change in NYHA classification from baseline will be summarized both with frequencies and percentages and as continuous data at 30 days, 6 months, 12 months, 18 months, 24 months and annually through five years.

For each subject with paired data, the number of classes changed from baseline (-3, -2, -1, 0, 1, 2, or 3) will be calculated at 30 days, 6 months, 12 months, 18 months, 24 months, and annually thereafter up to 5 years. For each treatment group, a Bayesian version of a paired t-test will be performed to evaluate change from baseline at 30 days, 6 months, 12 months, 18 months, 24 months, and annually through five years. The endpoint will be evaluated between groups using a Bayesian version of a t-test.

9. Change in distance walked during 6-minute walk test (6MWT) from baseline to 30 days, baseline to 12 months, and baseline to 24 months.

All subjects who are able to perform the six-minute walk evaluation at the time of the follow-up visit will be included in the analysis.

The endpoint will be evaluated using a Bayesian version of a t-test.

10. Ratio of days alive out of hospital versus total days alive assessed at 12 months and 24 months follow-up.

The proportion of post-procedure days alive out of hospital against total days alive will be compared between groups at 12 and 24 months. The numerator will be the number of days alive out of hospital, and the denominator will be the number of post-procedure days alive as of the last follow-up date. All hospitalizations will be included in this analysis, including hospitalization for device implant.

In addition, days alive out of hospital will be compared between groups at 12 months and 24 months.

The endpoint will be evaluated using a Bayesian version of a t-test.

11. Quality of Life (QoL) change from baseline at 30 days, 3 months, 6 months, 12 months, 18 months, 24 months, and annually thereafter up to 5 years.

The Kansas City Cardiomyopathy Questionnaire (KCCQ), SF-36, and EuroQoL will be assessed at baseline, 30 days, 6 months, 12 months, 18 months, 24 months, and annually thereafter up to 5 years. SF-36 and EuroQoL will also be assessed at 3 months. All subjects completing the questionnaires will be evaluated and the reasons for missing data will be provided.

The endpoint will be evaluated using a Bayesian version of a t-test.

12. Echocardiographic assessment of prosthetic valve performance at discharge, 6 months, 12 months, 24 months, and annually thereafter up to 5 years using the following measures:

- transvalvular mean gradient
- effective orifice area
- degree of prosthetic aortic valve regurgitation (including transvalvular and paravalvular)

The four echocardiographic measurements will be evaluated at discharge, 6 months, 12 months, 24 months, and annually thereafter up to 5 years. All implanted subjects undergoing echocardiography procedures will be evaluated.

Continuous measures will be evaluated using a Bayesian version of a two-sample t-test. Categorical variables will be evaluated using Bayesian version of a comparison of polytomous outcomes.

Additionally, incidence of moderate/severe aortic insufficiency at discharge will be compared between groups using the Bayesian version of a comparison of proportions.

13. Aortic valve disease related hospitalizations

The number of subjects re-hospitalized after the initial index procedure will be compared at 30 days, 6 months, 12 months, 18 months, 24 months, and annually thereafter up to 5 years.

Incidence of recurrent hospitalization will be provided at 30 days, 6 months, 12 months, 18 months, 24 months, and annually thereafter up to 5 years. The statistical method will be the Bayesian version of a comparison of proportions (with predictions).

14. Cardiovascular deaths and valve-related deaths

The number of subjects experiencing cardiovascular deaths and valve-related deaths at 30 days, 6 months, 12 months, 18 months, 24 months, and annually thereafter up to 5 years. Incidences will be compared between groups. The statistical method will be the Bayesian version of a comparison of proportions (with predictions).

15. Strokes and TIAs

The number of subjects with strokes (of any severity) and TIAs at 30 days, 6 months, 12 months, 18 months, 24 months, and annually thereafter up to 5 years. A separate analysis will be performed for each of the following:

- a composite of all strokes and TIAs
- disabling strokes only
- non-disabling strokes only
- TIAs only

The statistical method will be the Bayesian version of a comparison of proportions (with predictions).

Additionally, incidence of all strokes at 30 days or hospital discharge, whichever is longer, will be compared between groups using the Bayesian version of a comparison of proportions.

16. Peri-procedural Neurological Injury (Stroke, TIA, Encephalopathy)

For each treatment group, the proportion of subjects with a neurologic injury (stroke, TIA, or encephalopathy) at discharge or at 7 days post-index procedure (whichever occurs first) will be calculated. The numerator will be the number of subjects with a neurologic injury (stroke, TIA, or encephalopathy) at discharge or at 7 days post-index procedure (whichever occurs first), and the denominator will be the number of subjects in that treatment group. Results will also be presented separately for disabling stroke, non-disabling stroke, TIA, and encephalopathy. Proportions will be compared between groups using Bayesian version of a comparison of proportions.

17. Index procedure related MAEs

Index procedure-related MAE events will be summarized and event rates will be provided at 30 days. The numerator will be the number of procedure-related MAE events experienced by the end of the 30-day follow-up visit, and the denominator will be the number of subjects evaluated at the 30-day follow-up visit (or a later follow-up) plus the number of subjects not evaluated but who experienced a procedure-related MAE event prior to the end of the follow-up visit window.

Additionally, the percentage of subjects with a procedure-related MAE will be calculated in the same way, but allowing no more than one MAE per subject. The endpoint is descriptive and no statistical hypothesis test will be performed.

18. Length of index procedure hospital stay

The length of TAVI or SAVR hospital stay will be summarized for all subjects undergoing a study procedure.

The endpoint will be evaluated between groups using a Bayesian version of a t-test.

19. Presence of atrial fibrillation at post-procedure, discharge, 30 days, 6 months, 12 months, 18 months, 24 months, and annually thereafter up to 5 years.

The statistical method will be the Bayesian version of a comparison of proportions (with predictions).

The following secondary endpoints will be assessed for the TAVI cohort subjects only:

20. Device success defined as follows:

- Absence of procedural mortality AND
- Correct positioning of a single prosthetic heart valve into the proper anatomical location AND
- Intended performance of the prosthetic heart valve (no prosthesis-patient mismatch and mean aortic valve gradient <20 mmHg or peak velocity <3 m/s, AND no moderate or severe prosthetic valve regurgitation\*)
  - assessed acutely in a resting state, either within 24-48 hours after the index procedure or before hospital discharge

\*Refers to VARC-2 definitions

Device success, as defined above, will be calculated for all subjects undergoing the TAVI procedure.

The endpoint is descriptive and no statistical hypothesis test will be performed.

21. Procedural success, defined as device success and absence of in-hospital MACCE.
- Procedural success, as defined above, will be calculated for all randomized subjects undergoing the TAVI procedure.
- The endpoint is descriptive and no statistical hypothesis test will be performed.
22. Evidence of prosthetic valve dysfunction at 30 days, 6 months, 12 months, 24 months, and annually thereafter up to 5 years.
- The number of subjects with evidence of prosthetic valve dysfunction will be evaluated at 30 days, 6 months, 12 months, 18 months, 24 months, and annually thereafter up to 5 years.
- Point estimates and 95% BCIs for each time point will be presented using methods described below in the Bayesian version of a comparison of proportions (with predictions).
23. Resheath and Recapture (combined) success rate.
- The success rate will be analyzed for all subjects in whom the resheath or recapture feature is attempted. The number and percentage of successful resheath or recapture attempts combined will be calculated. Separate resheathing and recapturing success rates will also be calculated.
- The endpoint is descriptive and no statistical hypothesis test will be performed.
- Resheath and recapture success, as defined above, will be calculated for all subjects undergoing the TAVI procedure with Evolut R.

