The incidence of conduction disturbance requiring permanent pacemaker implantation will be provided at 30 days, 6 months, 12 months, 18 months, 24 months, and annually thereafter up to 5 years, separately for new onset and pre-existing conduction disturbance. The statistical method will be the Bayesian version of a comparison of proportions (with predictions).

5. Change in NYHA class from baseline at 30 days, 6 months, 12 months, 18 months, 24 months, and annually thereafter up to 5 years.

For each subject with paired data, the number of classes changed from baseline (-3, -2, -1, 0, 1, 2, or 3) will be calculated at 30 days, 6 months, 12 months, 18 months, 24 months, and annually thereafter up to 5 years. The endpoint will be evaluated using a Bayesian version of a t-test (or Wilcoxon test, as appropriate).

6. Change in distance walked during 6-minute walk test (6MWT) from baseline to 30 days, baseline to 12 months, and baseline to 24 months.

All subjects who are able to perform the six-minute walk evaluation; and those subjects who are unable to perform the walk evaluation due to heart failure symptoms at the time of the follow-up visit will be included in the analysis.

The endpoint will be evaluated using a Bayesian version of a t-test (or Wilcoxon test, as appropriate).

7. Ratio of days alive out of hospital versus total days alive assessed at 12 months and 24 months follow-up.

The proportion of post randomization days alive out of hospital against total days alive will be compared between groups at 12 and 24 months. The numerator will be the number of days alive out of hospital, and the denominator will be the number of days alive as of the follow-up visit date. All hospitalizations will be included in this analysis, including hospitalization for device implant.

The endpoint will be evaluated using a Bayesian version of a t-test (or Wilcoxon test, as appropriate).

8. Quality of Life (QoL) change from baseline at 30 days, 3 months, 6 months, 12 months, 18 months, 24 months, and annually thereafter up to 5 years.

The Kansas City Cardiomyopathy Questionnaire (KCCQ), SF-36, and EuroQoL will be assessed at baseline, 30 days, 6 months, 12 months, 18 months, 24 months, and annually thereafter up to 5 years. SF-36 and EuroQoL will also be assessed at 3 months. All subjects completing the questionnaires will be evaluated and the reasons for missing data will be provided.

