#### C.11.5 Continuous Data (Distribution-free, Superiority): Bayesian Version of a Wilcoxon Rank-Sum Test

For this test, data are ranked. Analogous to the Wilcoxon Rank-Sum test, observations in each group are replaced by their ranks in the combined order statistic. Then the two groups of rank-transformed data are compared via the Bayesian version of a t-test, above. It has been shown that conducting a two-sample t-test on rank-transformed data is approximately equivalent to the Wilcoxon Rank-Sum test.

Non-inferiority can be evaluated by first subtracting a margin ( $\delta$ ) from each observation in one treatment group prior to the rank transformation.

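### The six-minute walk comparison is selected on a post-randomisation outcome: subjects who have died or cannot attempt the walk at follow-up have no value in it

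*Combined protocol and SAP*

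**What the plan says.** The SAP in force is version 6.0. Item 9 of C.10 defines the endpoint as "Change in distance walked during 6-minute walk test (6MWT) from baseline to 30 days, baseline to 12 months, and baseline to 24 months". Its inclusion rule is: "All subjects who are able to perform the six-minute walk evaluation at the time of the follow-up visit will be included in the analysis". Its test is: "The endpoint will be evaluated using a Bayesian version of a t-test". C.11.4 builds that test from the mean, standard deviation and number of the observed values.

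Item 9 gives no value, rank or separate summary to a subject without a walk. Unlike the quality-of-life item (item 11), it does not undertake to report reasons for missing data.

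C.9.2 lists the 6MWT among the endpoints for which "inferential statistics for the following secondary endpoints will be performed on the ITT and mITT populations".

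C.11.5 keeps a rank-based method in which "observations in each group are replaced by their ranks in the combined order statistic", but item 9 does not call on it.

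The first SAP (item 6 of its C.10) also took in "those subjects who are unable to perform the walk evaluation due to heart failure symptoms at the time of the follow-up visit" and allowed a Wilcoxon-type test. That text is superseded. It is context, and the difference from the current text is not an error.

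**The concern.** Whether a subject is alive and able to attempt a walk at 30 days, 12 months or 24 months can depend on the treatment received. A set defined by that ability is no longer the set that was randomised. The subjects left out are largely those with the poorest functional result. If the arms differ in how many they lose, the arm that loses more looks better than it should.

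The result would be read as a comparison of exercise capacity between TAVI and SAVR. It is in fact a comparison among subjects who remained able to walk, and item 9 does not say so.

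**Working it through.** The documents give no power, standard deviation, margin or expected missing rate for the 6MWT, so there is no stated figure to reproduce. The check has four steps.

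**1. Does another section bring the missing subjects back?**

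- C.8 (missing data, shifted imputation, tipping point) is limited by its heading and content to the primary objective.
- C.11.3 (prediction from interim states) covers dichotomous outcomes only.
- C.11.4 uses observed values.
- C.9.2 names the ITT and mITT populations. Under C.3.2 these are all randomised subjects, and those with an attempted procedure. A subset able to walk at follow-up is neither.

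Nothing in the SAP fills the gap.

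**2. Who is lost?** In the walk-test instructions (Appendix R.14, Measurements), a subject who starts and then stops has the distance recorded, with the time and reason. Such subjects keep a value. The subjects lost are those who cannot attempt the test, those who have died, and those who do not attend.

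**3. How many are lost to death alone?** C.4.2 gives 1600 mITT subjects at 1:1, so 1600 / 2 = 800 per arm. Number lost = 800 × mortality.

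| Time point | Mortality and source | TAVI | SAVR |
|---|---|---|---|
| 30 days | 2.1% and 3.9% (Table 16, Appendix G.4) | 800 × 0.021 = 16.8 | 800 × 0.039 = 31.2 |
| 12 months | 10.9% and 13.2% (Table 16) | 800 × 0.109 = 87.2 | 800 × 0.132 = 105.6 |
| 24 months | about 15% assumed (C.4.2.1) | 800 × 0.15 = 120 | 800 × 0.15 = 120 |

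Table 16 describes an intermediate-risk subset of an earlier trial (239 TAVI and 205 SAVR subjects), not SURTAVI itself.

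**4. How far could inability among the living move the result?** This is an illustration on assumed values that are not in the documents. Let subjects able to walk gain g = 30 m in both arms, let B be mean baseline distance (200 to 400 m), and let p_T and p_C be the proportions unable to walk on TAVI and SAVR. For this illustration only, score inability as 0 m at follow-up, so that change = −B.

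- Difference among walkers: 30 − 30 = 0 m, whatever p_T and p_C are.
- Difference with everyone scored: [(1 − p_T)g − p_T·B] − [(1 − p_C)g − p_C·B] = (p_C − p_T)(g + B).

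| p_T vs p_C | B = 200 m | B = 300 m | B = 400 m |
|---|---|---|---|
| 5% vs 10% | 0.05 × 230 = +11.5 m | 0.05 × 330 = +16.5 m | 0.05 × 430 = +21.5 m |
| 10% vs 5% | −11.5 m | −16.5 m | −21.5 m |
| 2% vs 4% | 0.02 × 230 = +4.6 m | 0.02 × 330 = +6.6 m | 0.02 × 430 = +8.6 m |
| equal | 0 m | 0 m | 0 m |

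The shift depends on the imbalance between arms and can favour either arm.

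**The case against.** **The consequence is small.** The 6MWT is not among the 18 ordered objectives in C.12.1, and C.12 says that objectives outside the list will not support labeling claims. It has no margin or success threshold. This stands, and it limits the weight of the point.

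**Loss of function is visible elsewhere.** The clinical efficacy composite (C.10 item 5) counts death, stroke, hospitalisation for valve symptoms or worsening heart failure, and NYHA class III or IV. NYHA change, days alive out of hospital and KCCQ are also compared. A reader might infer that the plan conceals functional decline in the trial as a whole. The documents do not support that. The defect lies in the walk-test result.

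**The inclusion sentence does not exclude anyone in terms.** True, but a t-test on change needs a measured distance, and no rule supplies one. C.9.2 could be read as naming only the pool from which walkers are drawn. Even so, item 9 narrows that pool by outcome and does not say so.

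**The metre figures are hypothetical.** They are. It is tempting to set them against the 43 m in the appended walk-test statement, but that figure reflects individual patients' own rating of worsening and is not a benchmark for a difference between group means. It is not used here.

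**Scoring non-walkers as 0 m would not put them last.** Correct, because the endpoint is change. A subject with a 50 m baseline who becomes unable scores 0 − 50 = −50 m and ranks above a walker who falls from 300 to 200 m (−100 m). A subject scored 0 m at both visits has change 0 and ranks above every walker who declined. Restoring only heart-failure inability would also leave out deaths and other health-related inability. The fix must avoid both faults.

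**The main protocol may hold a rule.** I have not seen its main body. If a rule exists there, item 9 should cite it.

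**Conclusion.** The point holds. As written, item 9 compares change in walk distance in a set selected after randomisation by survival and ability to walk, and this does not match the inference stated in C.9.2.

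The loss from deaths alone is about 120 of 800 per arm at 24 months, if the SAP's 15% assumption is right. The number of living subjects unable to attempt the walk is unknown, so neither the direction nor the size of bias can be stated. The range of 11.5 to 21.5 m for a 5-point imbalance rests entirely on the assumed gain, baseline distance and inability rates.

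A reader might infer that the rule favours TAVI, or that non-walkers were dropped after the first SAP to improve the result. Nothing in the documents shows either. The bias can run both ways, and the first SAP gave no scoring rule for such subjects.

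The consequence is confined to a secondary result that supports no claim. The change is worth making because it is cheap and the result will be reported.

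**What to change.** In item 9 of C.10:

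- Add a prespecified rank-based comparison using C.11.5. Assign the worst ranks directly: death lowest, then inability to attempt the walk for health reasons, then walkers ordered by change in distance. Do not derive a change score from 0 m.
- State how subjects unable to walk at baseline are handled.
- Report by arm and visit the numbers with no walk and the reasons.
- Keep the mean change among walkers, labelled as conditional on being able to walk.
- Align the wording of item 9 with C.9.2.

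The cost is mainly SAP wording, since the method is already specified. There are two small downsides. The rank result is not in metres and combines survival with function, which is why the conditional mean stays beside it. The sponsor must also confirm that the case report form records why a walk was not attempted: the worksheet in Appendix R.14 asks for a reason only when a walk is stopped or paused early, and the case report forms are supplied separately (Appendix R.5).
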